## **DATA ANALYSIS**

**Biomechanical Data Analysis:** All data will be recorded and analyzed off-line using custom-scripts in Matlab using the Chronux toolbox to examine changes in oscillatory neural activity time-locked to FOG episodes identified with the kinematic data from the body worn motion sensors in the motion capture area. The 3D position data of each foot will be utilized to determine steps and other biomechanical stepping variables FOG episodes will be identified utilizing the data from the body-worn motion sensors.

**Neural Data Analysis:** Neural data will be detrended and passed through a moving window line noise subtraction algorithm to remove drifting baseline and continuous noise artifacts, respectively. From the Percept device, 6 electrode pair combinations, 3 combinations per DBS lead, will be recorded directly with the Percept communicator. Windows containing movement artifacts will be visually identified by large fluctuations in the time series and high amplitude broadband activity in the spectrogram and removed from further analysis. Triggered spectrograms will be calculated for each trial using the multi-taper method with a 100 ms, 50 ms overlap moving window, 2.5 Hz frequency resolution, and 1 taper.

**Local Field Potential (LFP) Outcomes:** The relationship of synchronization and desynchronization changes in oscillatory activity within the delta, theta, alpha, beta and/or gamma bands as well as the power of high-frequency oscillations (200+ Hz) will be calculated in relation to all events identified with the kinematic data, i.e. normal walking and FOG episodes. Power spectral densities will be used to determine the power and confidence bands of oscillatory activity across frequencies during these events.

**Statistical Analysis:** Neural data outcomes, average power within alpha, beta, and/or gamma frequency bands, will be quantified using descriptive statistics during FOG episodes and during periods of functional walking while performing the V-Gait modules. Within and across participant analyses will determine the degree of consistency and similarity of the neural signal during FOG episodes between each medication state (ON and OFF).

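### The two paragraphs that define the neural outcomes list different frequency bands, *and/or* leaves the reported band open, and the stated 100 ms window cannot resolve delta or theta

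*Combined protocol and SAP*

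**What the plan says.** All the relevant text is in the DATA ANALYSIS section of the combined protocol and SAP.

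- **LFP Outcomes** covers synchronisation and desynchronisation in five bands, given as "oscillatory activity within the delta, theta, alpha, beta and/or gamma bands". To these it adds oscillation power at 200+ Hz. Each is to be related to the kinematically detected events, which are FOG and normal walking. A further sentence reads: "Power spectral densities will be used to determine the power and confidence bands of oscillatory activity across frequencies during these events".
- **Statistical Analysis** identifies the neural data outcomes as "average power within alpha, beta, and/or gamma frequency bands". The treatment planned for them is that they "will be quantified using descriptive statistics during FOG episodes and during periods of functional walking". Its closing sentence, on ON versus OFF medication, speaks of the neural signal in general and names no band or metric.
- **Neural Data Analysis** computes the triggered spectrograms "with a 100 ms, 50 ms overlap moving window, 2.5 Hz frequency resolution, and 1 taper". It records six electrode pairs, three per lead.

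The document gives no band limits in Hz, no lead band, no rule for resolving *and/or*, and no rule for selecting or combining electrode pairs. It names no test, model or alpha level.

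**The concern.** The paragraph that says what will be calculated and the paragraph that says how it will be summarised give different lists. An analyst working from Statistical Analysis has no instruction for delta, theta or 200+ Hz power. For alpha, beta and gamma, the analyst may report one, two or all three.

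This matters because of the objective, which is to identify the neural signatures of FOG. Which band carries the signature is the main result of the study. If the band shown is the one that happened to differ most, its difference is overstated, and a reader of the report cannot tell that a choice was made. This happens whether or not a p-value is attached.

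Copying the longer list into Statistical Analysis would not be enough, because the stated spectrogram window is too short for the two lowest bands.

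**Working it through.** The plan states no effect size, SD, alpha or sample-size calculation on this point, so it has no figure of its own to reproduce.

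**1. Count of outcomes**

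| Outcome | LFP Outcomes | Statistical Analysis |
|---|---|---|
| delta | listed | not named |
| theta | listed | not named |
| alpha | listed | listed |
| beta | listed | listed |
| gamma | listed (*and/or*) | listed (*and/or*) |
| 200+ Hz power | listed, outside the *and/or* | not named |

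Three of the six named outcomes (3/6 = 50%) are absent from Statistical Analysis. Read as any non-empty choice, *and/or* over three bands permits 2³ − 1 = 7 different selections.

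**2. Effect of choosing the band afterwards**

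Input from the document: n = 15. Assumptions: every participant contributes one FOG-minus-walking difference per band, differences are normal, there is no true effect, and the bands are equally correlated at 0 to 0.8. The document gives no correlation. The summary is d = mean difference / SD of differences, so that d = t/√15 with t on 14 degrees of freedom.

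- One band fixed in advance: E|d| = E|t₁₄|/√15 = 0.844/3.873 = 0.22.
- Largest of three independent bands: E(max|d|) = (1/√15) ∫₀^∞ {1 − [2F₁₄(x) − 1]³} dx = 0.37, where F₁₄ is the t distribution function.
- Largest of three bands at correlation 0.8, by simulation: 0.31.
- Inflation over a fixed band: 0.31/0.22 = 1.4 to 0.37/0.22 = 1.7 times.

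A 95% interval for one band has half-width t(0.975, 14)/√15 = 2.145/3.873 = 0.55 SD. The chance that at least one of three such intervals excludes zero is:

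- independent bands: 1 − 0.95³ = 0.143, about 14%;
- correlation 0.8, by simulation: about 10%;
- one band fixed in advance: 5%.

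**3. Spectrogram window**

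- Basic resolution of a window of length T is 1/T. For T = 0.1 s this is 1/0.1 = 10 Hz.
- A resolution of 2.5 Hz needs T = 1/2.5 = 0.4 s, four times the stated window.
- Cycles held in 0.1 s are f × 0.1. With assumed limits of 1–4 Hz for delta and 4–8 Hz for theta, that is 0.1 to 0.4 cycles for delta and 0.4 to 0.8 for theta. Neither band completes one cycle.

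**The case against.** **The second list may be a deliberate subset.** One paragraph says what is computed and the next says which averages are tabulated; nothing in the second excludes the rest. LFP Outcomes also uses *and/or*, so six firm outcomes is only one reading. This is fair, and the fault is better called an inconsistency than a direct contradiction. It does not settle the matter, since on this reading neither paragraph fixes the bands. The 200+ Hz power stands outside the *and/or* and still has no summary in Statistical Analysis.

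**The omitted outcomes are not abandoned.** A reader might infer that delta, theta and 200+ Hz are never analysed. The document does not support that: LFP Outcomes commits to calculating them against walking and FOG events, and to power and confidence bands across frequencies. What is missing is a stated FOG-versus-walking summary in Statistical Analysis.

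**The study is descriptive.** With no test or alpha there is no formal type I error rate to breach, and the interval-based percentages describe a criterion that the plan does not adopt. That stands, and they are illustrative only. The inflation of the largest difference does not depend on a test.

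**Larger figures are tempting.** Three bands by six electrode pairs gives 18 cells and 1 − 0.95¹⁸ = 60%; both medication states give 36 cells and 1 − 0.95³⁶ = 84%. These assume independent cells and that a pair and a state are also picked for their result. The document does not say that they will be, so these are not the size of the band-choice problem. Correlation lowers them considerably: at 0.8, the 18-cell figure is 23%. They do show that the risk grows if pairs or states are selected too.

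**The 100 ms window is stated only for triggered spectrograms.** This is correct. No window is given for the power spectral densities, so low-band power might be obtainable there. The window point is limited to time-locked changes.

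**Conclusion.** The concern holds in limited form. The two paragraphs give different outcome sets, three of the six named outcomes lack a stated FOG-versus-walking summary in Statistical Analysis, and the band reported can be chosen after the data are seen. The consequence is selective reporting in a descriptive study: chance alone would make the highlighted band look about 1.4 to 1.7 times as large as a band fixed in advance (0.31 to 0.37 against 0.22 SD).

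These sizes rest on 15 contributing participants, no true effect, one difference per band and correlation between 0 and 0.8. If some participants have no FOG episodes in a session, fewer contribute and the chance differences are larger.

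The window finding is separate and is arithmetic. A 100 ms window does not deliver 2.5 Hz resolution and cannot give time-locked delta or theta changes, if those bands lie at about 1–8 Hz. Whether the power spectral densities can supply those bands cannot be judged from the document.

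**What to change.** 1. Put one fixed band list, with limits in Hz, in both LFP Outcomes and Statistical Analysis, and delete *and/or* from both.
2. State that the FOG-minus-walking change will be reported for every listed band, electrode pair and medication state, whatever the result. Label all of these exploratory unless a lead band is named before the data are examined. If data have already been examined, say so and still report every band.
3. Reconcile the spectrogram settings. Either compute delta and theta from a longer window (about 0.4 s or more for 2.5 Hz resolution, and longer for delta, since one cycle at 1 Hz lasts 1 s) or remove them from the list. State the window used for the power spectral densities.

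The cost is wording, analysis time and a larger results table: with all six outcomes, 6 bands × 6 pairs × 2 states = 72 entries; without delta and theta, 4 × 6 × 2 = 48. A longer window also gives coarser timing of low-band changes around FOG onset. No new participants or recordings are needed.

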# ClinicalTrials.gov Final Outcomes Report

NCT Number:	05103384
Project Title:	Utilizing Neural Signatures and Virtual Reality to Advance DBS Programming
Principal Investigator Name:	[name]
Principal Investigator Organization and Address:	Cleveland Clinic [name]
Document Date:	9/27/2023

**Title:** Utilizing Neural Signatures and Virtual Reality to Advance DBS Programming

**Primary Investigator:** [name]

**Study Funder:** Michael J. Fox Foundation for Parkinson's Research

**Protocol Date:** 9/27/2023

**PROJECT GOAL:** Falls related to postural and gait impairments and freezing of gait (FOG) occur in nearly 80% of Parkinson's disease (PD) patients and are the greatest motor-related contributor to health care costs and the primary reason for transition to dependent care settings among PD patients. Despite their prevalence in the daily lives of PD patients, identifying FOG episodes in a clinical or laboratory environment is challenging. Consequently, the neural signature underlying FOG remains elusive. A necessary step in treating FOG is characterizing neural activity within the basal ganglia during FOG episodes. An approach to evaluate the neural signals associated with FOG includes recording the neural activity in the area of the subthalamic nucleus (STN) or globus pallidus internus (GPi) from implanted deep brain stimulation (DBS) leads. The proposed project combines the most advanced virtual reality (VR) technology and neural recording techniques to identify specific neural correlates of FOG while patients physically walk through a virtual environment, Virtual-Gait Task (V-GAIT), that simulates motor and cognitive\limbic triggers.

**Objective:** To identify the corresponding neural signatures of FOG associated with motor and cognitive\limbic triggers.

Fifteen individuals with PD will complete the V-GAIT modules while synchronized kinematic and neural data from the DBS lead within the STN or GPi are recorded. The kinematic data will be utilized to identify the timing of FOG episodes in the neural data. The neural correlates of FOG in the ON and OFF medication states within each domain will be evaluated.

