## METHODOLOGY AND APPROACH

The V-GAIT platform utilizes a VR headset to deliver high fidelity realistic virtual environments resembling a home environment while the participant walks on an omnidirectional treadmill. Briefly, the VR headset provides a realistic display with high resolution and refresh rate, wide field of view, and color clarity currently available. The 360-degree moving platform allows the user to naturally walk and turn in any direction. The 3-dimensional linear and angular position of the head, waist, and both feet are tracked using motion sensors that are embedded in the headset, waist belt, and foot straps. To ensure safety, a supported harness is worn by the user. To monitor overall exertion and provide a proxy for stress, a heart rate monitor is integrated into the V-GAIT platform.

**V-GAIT Module:** This module replicates a home, including a kitchen. The tasks will include, but not be limited to, walking in hallways will have digital doorways which reduce the width of the passageway and a virtual room where participants will appear to walk on an elevated platform to trigger anxiety-induced FOG.

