## DATA COLLECTION PROCEDURES

**Neural Recording Procedures:** The proposed study design will enable synchronized recordings to be made in the form of LFP from the six or eight channels of implanted DBS lead(s), as well as IMU sensors from the V-GAIT platform to quantify gait-related behaviors using a commercial EEG recording platform. The physiological and sensor data will be synchronized to motor task and gait-related activities and events associated with participant performance on the V-GAIT paradigm through additional analog and digital ports using a low voltage electrical current (1.5 mA) through surface electrodes placed on the participant's neck.

**Behavioral Tasks:** The Unified Parkinson's Disease Rating Scale (UPDRS) will be conducted by a rater blinded to medication state.

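### The walking reference for FOG band power is not restricted by scene, so the FOG-walking difference may include the response to the trigger itself

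*Combined protocol and SAP*

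**What the plan says.** The objective, on the opening page of the combined protocol and SAP, is "To identify the corresponding neural signatures of FOG associated with motor and cognitive\limbic triggers". The same page adds: "The neural correlates of FOG in the ON and OFF medication states within each domain will be evaluated".

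Methodology and Approach describes a virtual home with a kitchen. Of the motor trigger it says: "walking in hallways will have digital doorways which reduce the width of the passageway". The anxiety trigger is "a virtual room where participants will appear to walk on an elevated platform to trigger anxiety-induced FOG". The task list is expressly not exhaustive.

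In Data Analysis, the LFP outcomes are calculated "in relation to all events identified with the kinematic data, i.e. normal walking and FOG episodes". The events are thus defined by movement alone. The Statistical Analysis paragraph then states that average band power "will be quantified using descriptive statistics during FOG episodes and during periods of functional walking while performing the V-Gait modules". It does not mention scene or trigger. Its other stated comparison is the consistency of the FOG signal between the ON and OFF medication states.

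Data Collection Procedures says that the physiological and sensor data will be "synchronized to motor task and gait-related activities and events associated with participant performance on the V-GAIT paradigm".

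**The concern.** A signature of freezing should separate freezing from walking under otherwise similar conditions. Here the two sets of windows may differ in two ways: whether the participant is frozen, and whether the participant is facing a narrow doorway or an apparent drop. The more successfully the scenes provoke freezing, the more FOG windows fall inside them, and the further the sets may differ in exposure.

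A change in band power caused by fear on the platform, or by the sight of a narrow passage, could then be reported as part of the FOG signature. The objective ties signatures to trigger types, and the project aims to inform DBS programming, so this attribution matters.

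**Working it through.** The plan gives no effect size, variance or expected number of episodes, so it has no figure to reproduce. The check has two parts.

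**1. Does any text fix the source of the walking windows?**

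- *Statistical Analysis* limits walking only to time spent in the V-GAIT modules.
- *LFP Outcomes* defines events by kinematics; scene is not part of the definition.
- The *opening page* promises evaluation within each domain. That sentence is about the correlates of FOG, does not mention walking, and is not carried into Statistical Analysis.
- *Biomechanical and Neural Data Analysis* plan activity aligned in time to FOG episodes and triggered spectrograms, but state no baseline period.

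None of these settles the point.

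**2. What follows if walking is not matched by scene?**

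Let m be mean band power when walking outside trigger scenes, F the effect of freezing, and T the effect of being in a trigger scene. Let pF and pW be the shares of FOG and walking windows inside trigger scenes. With additive effects:

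- mean in FOG windows = m + F + pF × T
- mean in walking windows = m + pW × T
- difference = F + (pF - pW) × T

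F, T, pF and pW are not in the documents. The pairs below are assumptions that show the range only.

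| pF | pW | Bias |
|---|---|---|
| 0.5 | 0.5 | 0 |
| 0.5 | 0.7 | -0.2T |
| 0.9 | 0.7 | 0.2T |
| 0.7 | 0.4 | 0.3T |
| 0.9 | 0.2 | 0.7T |
| 1.0 | 0.2 | 0.8T |

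The bias is zero only if T = 0 or pF = pW. If F = 0, the bias is the whole observed difference. A small pW cannot be taken for granted: the hallways themselves contain the narrowed doorways, and nothing says that the kitchen is free of triggers.

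On T, the documents give no value. The design does allow for a stress response, since heart rate is monitored partly as a proxy for it.

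**3. What would matching achieve?**

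If FOG and reference windows both come from the same trigger type, pF = pW = 1 and the term becomes (1 - 1) × T = 0. This assumes that freeze and non-freeze passes are otherwise alike. If the response to the trigger differs between them by D, for example because calmer passes are less likely to end in a freeze, the matched difference is F + D.

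**The case against.** There are four serious replies.

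*The plan is silent on the source of walking; it does not plan to pool.* This is correct. A reader might infer that walking is deliberately drawn from the whole module, or mainly from trigger-free hallways. The documents support neither. The definition is merely unrestricted, and the hallways contain the doorway trigger. Evaluation within domain could also be meant to include walking from that domain. What stands against the plan is that it does not say so, and that even walking within a domain could mix trigger and non-trigger segments.

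*The analysis aligned to FOG onset is local in time.* Activity just before a freeze would often come from the same or an approaching scene. That helps, but with no baseline stated it does not settle the reference, and the band-power summary remains a separate planned output.

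*The response to the trigger may belong to the target.* The objective concerns FOG associated with triggers, so part of that response may be of interest. This is a fair reason not to make the matched contrast the sole main one. It is also a reason to report the trigger response separately.

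*No test is affected.* The analysis is descriptive, so no stated error rate is inflated. Nor do the documents show that the ON-OFF comparison is biased, since both sessions use V-GAIT. The risk is misattribution in the reported signature.

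**Conclusion.** The point holds as a gap in specification with a plausible direction. Because the scenes are designed to provoke freezing, FOG windows are likely to be over-represented in them, and the planned FOG-walking difference may then include the response to the trigger. Under additivity the bias is (pF - pW)T. Its size cannot be determined from the documents, and it could be nil.

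A reader might go further and put a percentage on the overstatement, or conclude that the reported signature would be an anxiety response. Either step needs values for T, pF and pW that the plan does not give. A reader might also infer that matching by scene removes the problem. It does so only if effects are additive and freeze and non-freeze passes at the same trigger are otherwise alike. The change is a cheap improvement to an exploratory analysis; the planned comparison need not be discarded.

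**What to change.** In Statistical Analysis, before windows are selected:

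1. State where the functional-walking windows come from, and label every FOG and walking window by scene (doorway, elevated platform, outside trigger zones), using the tracked position and the V-GAIT event synchronisation.
2. Keep the planned comparison of FOG with all functional walking.
3. Beside it, report FOG against the same participant's non-freeze walking through the same trigger type in the same session.
4. Report walking in trigger zones against walking outside them, as a description of the trigger response itself.

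**Cost.** The change is SAP wording and a scene label. It should need no new data, but the team should confirm that location in the virtual scene is stored, which the documents do not say outright. The number of passes per trigger is also not given.

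**Downsides to state in the plan.** There will be fewer reference windows, in a study of fifteen participants. A participant who freezes on every pass at a trigger has no matched reference there and, for that trigger, contributes only to the all-walking comparison. Non-freeze passes may still differ in anxiety, so the matched contrast reduces the confounding but may not remove it.
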